3.5.6.24.1. Blood Samples for Pharmacokinetic Assessments

Blood samples for the quantification of plasma JTE-051 will be collected, according to the schedules summarized in [Table 1](#). Trough PK blood samples will be collected in the fasted state at pre-specified study visits.

The actual date and time of the last dose of study drug prior to the PK sample collection, as well as the sample collection date and time will be documented for PK data analysis. Refer to the laboratory manual for specific instructions for the collection, processing, storing and shipping of blood samples for PK assessments.

[figure not shown]
3.5.6.24.2. Analysis of JTE-051 in Plasma

JTE-051 in plasma will be analyzed using a validated LC-MS/MS method.

The laboratory performing the JTE-051 plasma concentration assessments will be unblinded to facilitate analysis of only the samples from the JTE-051-treated subjects. Plasma samples from placebo subjects may be analyzed as needed.

3.6. Adverse Events

3.6.1. Safety Definitions

Akros complies with the following International Conference on Harmonisation (ICH) AE definitions:

Adverse Event: An AE is any untoward medical occurrence in a patient or clinical investigation subject administered a pharmaceutical product and which does not necessarily have a causal relationship with this treatment. An AE can therefore be any unfavorable and unintended sign (including an abnormal laboratory finding), symptom, or disease temporally associated with the use of a medical (investigational) product, whether or not related to the medical (investigational) product.

Serious Adverse Event: As provided by the ICH criteria, an SAE is any adverse drug experience occurring at any dose that results in any of the following outcomes:

- death
- a life-threatening adverse drug experience
- inpatient hospitalization or prolongation of existing hospitalization
- a persistent or significant disability/incapacity
- a congenital anomaly/birth defect
- other important medical event

Note: Important medical events that may not result in death, be life-threatening, or require hospitalization may be considered a serious adverse drug experience when, based upon appropriate medical judgment, they may jeopardize the patient or subject or may require medical or surgical intervention to prevent one of the outcomes listed in this definition. Examples of such medical events include allergic bronchospasm requiring intensive treatment in an emergency room or at home, blood dyscrasias or convulsions that do not result in hospitalization, or the development of drug dependency or drug abuse.

Adverse Reaction: All noxious and unintended responses to an investigational medicinal product (IMP) related to any dose administered.

Note: The phrase "responses to a medicinal product" means that a causal relationship between the medicinal product and an adverse event is at least a reasonable possibility, i.e., the relationship cannot be ruled out.

Unexpected Adverse Drug Reaction: An adverse reaction, the nature (specificity) or severity of which is not consistent with the applicable product information (e.g., Investigator's Brochure).

Death: Death represents an outcome and a SAE criterion, not an event term. The medical condition with the fatal outcome should be reported unless the cause of death is unknown, in which case the term "Death" is acceptable.

Inpatient Hospitalization/Prolongation of Hospitalization: Any admission (even if less than 24 hours) to a healthcare facility. Admission also includes transfer within the hospital to an acute/intensive care unit (e.g., medical floor to the coronary care unit). Initial and prolonged hospitalizations that **do not** meet this SAE criterion include those due to social and/or convenience reasons (e.g., lack of personal care at home, unable to transfer to non-acute facility), admission to rehabilitation/hospice/skilled nursing facilities, emergency room visits, same-day/outpatient/ambulatory procedures, and those for pre-planned, elective procedures for a pre-existing condition that did not worsen after the informed consent has been signed (no AE present). However, if the hospitalization was prolonged due to a complication of a pre-existing condition, the complication (diagnosis of same) would qualify as an SAE.

Disability: A substantial disruption of a person's ability to conduct normal life functions.

Life-threatening: Any adverse drug experience that places the patient or subject, in the view of the Investigator, at immediate risk of death from the reaction as it occurred, i.e., it does not include a reaction that had it occurred in a more severe form, might have caused death.

Physical Examination, [REDACTED] Vital Signs, Laboratory Test and ECG Abnormalities: Any abnormalities fulfilling the criteria for an SAE should be reported as such, in addition to being recorded as an AE in the CRF. Any abnormal vital sign, physical [REDACTED] finding or laboratory/ECG result which is clinically significant (i.e., meets one or more of the following conditions) should be recorded as a single diagnosis on the AE page in the CRF:

- Accompanied by clinical symptoms
- Leads to permanent discontinuation of study drug
- Requires a change in concomitant therapy (e.g., addition of, interruption of, discontinuation of, or any other change in a concomitant medication, therapy or treatment).

This does not apply to abnormal vital signs, physical finding or laboratory/ECG results that do not meet the clinical significance criteria or those which are a result of an AE which has already been reported.

Pre-existing conditions that are detected at the Screening Visit (Visit 1), including abnormalities in ECG, physical examination, [REDACTED] vital signs, and laboratory tests, are considered to be medical history.

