3.4. Removal of Subjects from the Study

[figure not shown]
A subject will not participate further in the study under the following conditions:

1. Withdrawal by Subject: subjects have the right to withdraw from the study at any time. However, if a subject withdraws consent because of experiencing an adverse event, the reason for subject termination should be documented as the adverse event.
2. Adverse Event: a clinical or biological adverse event or intercurrent condition(s), requiring study drug discontinuation, whether or not related to the study drug

If grade 3 findings (defined as severe or medically significant but not immediately life-threatening; hospitalization or prolongation of hospitalization indicated; disabling; limiting self-care activities of daily living [ADL] such as bathing, dressing, undressing, feeding self, using the toilet, taking medication, but not bedridden), according to the CTCAE²⁵, are noted in a subject, he/she must be promptly evaluated by the Investigator (including repeat tests, evaluation of the baseline parameters, concomitant medications, etc.) for potential withdrawal from the study. Every effort should be made to discuss with the study's Medical Monitor prior to final decision, unless not feasible, based on safety considerations. Subjects who interrupted study drug administration due to a grade 3 CTCAE finding may be re-started on therapy if the event has resolved and it is considered appropriate by the Investigator and Sponsor or designee.

Notes:

- The investigator may decide to evaluate or withdraw the subject from the study based on findings of lesser than grade 3 severity, according to his/her judgment.

3. Consistent* Non-compliance with Study Drug (i.e., <80% or >120% compliance; exceptions on a case-by-case basis may be permitted if approved by Sponsor or designee)

*Determined at >1 study visit during the Treatment Period. If compliance of <80% or >120% is identified at a study visit, the Investigator or designee is to counsel the subject and ensure steps are taken to improve compliance.

4. Inclusion/Exclusion Criteria Not Met: the subject was randomized in the study and did not meet all inclusion/exclusion criteria mandated by the protocol (exceptions on a case-by-case basis may be permitted if approved by Sponsor or designee)

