3.6.2. Assessing Adverse Events

When completing appropriate forms for reporting the AE, the Investigator will be asked to assess the AE as follows:

Seriousness of Adverse Event:

- Serious: The AE meets a criterion of the SAE definition.
- Not Serious: The AE does not meet a criterion of the SAE definition.

Severity of Adverse Event:

- Mild: No interference with functioning.
- Moderate: No significant interference with functioning.
- Severe: Significant interference with functioning.

Relationship of Adverse Event (Causality):

The Investigator's causality assessment is the determination whether there is a reasonable possibility that the IMP caused or contributed to the adverse event. Generally, the facts (evidence) or arguments to suggest causal relationship should be documented. Factors to be taken into consideration when assessing causality include: subject's underlying and pre-existing conditions, prior/concomitant medications, timing of onset relative to study drug administration, the known PK characteristics of JTE-051, the currently-known safety profile of JTE-051, known class effects of similar MOA drugs, the de-challenge/re-challenge response (if available) and any other information that is considered relevant by the Investigator.

Akros Pharma Inc. evaluates the relationship of an AE to the study drug using the following three categories:

- Not Related
- Possibly Related
- Related

Action Taken with Regard to Study Drug:

Akros Pharma Inc. evaluates the action taken with the treatment product and/or interacting product using the following four definitions:

- Dose Not Changed: The subject was on treatment with the study drug when the AE occurred, and the study drug dosing was maintained at the same dose level
- Drug Interrupted: The subject was on treatment with the study drug when the AE occurred, and the study drug dosing was temporarily discontinued and then re-started
- Drug Withdrawn: The subject was on treatment with the study drug when the AE occurred, and the study drug dosing was permanently discontinued
- Not Applicable: The subject was not receiving treatment with the study drug when the AE occurred (i.e., AE occurred before the first study drug administration or after the last study drug administration)

Other Action Taken:

- None
- Additional Treatment Given for the AE
- Therapeutic/ Diagnostic Procedure
- Other (including discontinuation/reduction of a concomitant medication due to the AE)

Outcome to Date:

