6.5.1 Adverse Events (AEs)

The number and percentage of subjects experiencing TEAEs will be tabulated by treatment according to the following categories:

- Overall summary of TEAEs.
- TEAEs by system organ class and preferred term.
- TEAEs leading to study discontinuation by system organ class and preferred term.
- TEAEs by system organ class, preferred term and AE severity.
- TEAEs by system organ class, preferred term and AE causality.
- TEAEs by preferred term (in order of descending frequency in the total JTE-051 group).
- Serious AEs (SAEs) by system organ class and preferred term.
- Serious AEs leading to study discontinuation by system organ class and preferred term.

Listings will be provided for SAEs and AEs leading to study discontinuation.

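### Protocol 3.6.1 does not require an adverse event record for a symptom-free, non-serious abnormal result that leads to interruption and restart of study drug

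*Protocol*

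**What the plan says.** Protocol 3.6.1 sets the rule for abnormal vital signs, physical findings, laboratory results and ECGs. A clinically significant result goes on the AE page, and clinical significance is defined as meeting at least one of three conditions:

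- The first is the presence of symptoms.
- The second concerns study drug: "Leads to permanent discontinuation of study drug".
- The third concerns other treatment: "Requires a change in concomitant therapy (e.g., addition of, interruption of, discontinuation of, or any other change in a concomitant medication, therapy or treatment".

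The following paragraph closes the list: "This does not apply to abnormal vital signs, physical finding or laboratory/ECG results that do not meet the clinical significance criteria". Separately, and before the list, 3.6.1 says that an abnormality meeting a serious adverse event (SAE) criterion is reported as an SAE and also recorded as an AE.

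Other sections bear on the same case:

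- Protocol 3.4, in the item on withdrawal for an AE, requires prompt evaluation of grade 3 findings and adds: "Subjects who interrupted study drug administration due to a grade 3 CTCAE finding may be re-started on therapy", provided the event has resolved and the investigator and sponsor agree.
- Protocol 3.6.1, in the general AE definition, counts an abnormal laboratory finding among the things that can be an AE.
- Protocol 3.6.2 offers a Drug Interrupted action for an AE, where "the study drug dosing was temporarily discontinued and then re-started", and names the response to de-challenge and re-challenge as a factor in judging causality.
- SAP 6.5.1 lists eight tabulations. One is "TEAEs leading to study discontinuation by system organ class and preferred term". None is for interruption of study drug.

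**The concern.** The list treats two kinds of interruption differently. If a background medicine is held because of a laboratory result, the third condition makes that result an AE. If the investigational drug is held for the same result and later restarted, no condition is met. The protocol gives no reason for the difference.

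The case is not far-fetched, because 3.4 describes it. Protocol 1.3 presents this as the first study in patients, notes the hepatic and renal toxicity of background methotrexate, and mentions hepatic signals with comparable compounds. Four active doses are compared with placebo. A laboratory finding that leads to a hold, recovers and is followed by a restart carries information on causality. If no AE is recorded, the investigator's causality judgement, the action taken and the outcome have no assigned place in the safety data.

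**Working it through.** No figure in the plan is at issue, so the check is mainly a reading of the sections against one test case: a non-serious abnormal result without symptoms, study drug held, result recovered, study drug restarted, no other treatment changed.

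**1. The three conditions in Protocol 3.6.1**

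| Condition | Test case | Met? |
|---|---|---|
| Symptoms | None | No |
| Permanent discontinuation of study drug | Held, then restarted | No |
| Change in concomitant therapy | None; the interruption named here is of other treatments | No |

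None is met, so the closing paragraph takes the result outside the recording rule. The third condition is also less likely to catch such cases than it looks, because Protocol 3.5.4.1 says the methotrexate dose and route must not change until after the follow-up visit.

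**2. The SAE route.** This applies whatever the three conditions say. It includes the important-medical-event category, which rests on medical judgement, and 3.6.1 gives blood dyscrasias without hospitalization as an example. The test case is therefore limited to results that are not judged serious.

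**3. The other sections.** Protocol 3.4 deals with the interruption under the AE heading and calls it an event. Protocol 3.6.2 has the action category and the causality factor that the case would need. The general definition in 3.6.1 admits a laboratory finding as an AE. Each presupposes a record that the closed list does not require. Nothing else in the readable text adds study-drug interruption as a recording trigger.

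**4. What the other outputs keep**

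- *Value:* SAP 6.5 and 6.5.3 to 6.5.5 summarise treatment-emergent potentially clinically significant (PCS) laboratory, vital-sign and ECG values by arm. SAP Table 3 counts ALT and AST at 3, 5, 10 and 20 times the upper limit of normal.
- *Hold:* SAP 5.3.5 defines compliance as tablets taken / (treatment duration × 4) × 100. Over 12 × 7 = 84 days, full dosing is 84 × 4 = 336 tablets. If held days count in the duration, an assumed 7-day hold gives (77 × 4)/336 = 308/336 = 91.7%. A 16-day hold gives (68 × 4)/336 = 272/336 = 81.0%, and a 17-day hold gives (67 × 4)/336 = 268/336 = 79.8%. So a hold of up to 16 days, with no other missed dose, stays inside the plan's 80–120% band for the whole period. If held days are left out of the duration, the hold does not show at all. SAP 5.3.5 does not say which applies. Between-visit compliance would fall further, but neither measure separates an instructed hold from missed doses.
- *Link:* no specified output joins the value, the hold, the causality judgement and the outcome. The AE record would do that.

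**5. If the site records it anyway.** The case enters the general TEAE tables, including those by severity and causality, and SAP 7 lists all eCRF data, so the Drug Interrupted action would appear in a listing. No table or dedicated listing gathers such events. On the functional scale in 3.6.2 ("Mild: No interference with functioning") a symptom-free result would be rated mild, whatever its CTCAE grade.

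**6. Unit of size.** With 50 subjects per arm, one unrecorded subject is 1/50 = 2 percentage points of that arm's TEAE incidence, if the subject has no other TEAE.

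**The case against.** The strongest reply is that this is a small wording gap with little practical effect. The closing paragraph limits what must be recorded and forbids nothing. A site that reads the general AE definition together with 3.4 could reasonably record the case and tick Drug Interrupted. The more serious findings may come in as SAEs. The values are tabulated by arm whether or not an AE is recorded, and compliance and exposure are summarised by arm. The change in concomitant therapy is a broad trigger, so the residual case is narrow.

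Much of this stands, and it rules out several readings that might be inferred. A reader might infer that such results are never recorded as AEs; the text supports only that recording is not required. A reader might infer that the three conditions are the sole route to the AE page; the SAE route is separate. A reader might infer that SAP 6.5.1 tabulates only events leading to discontinuation; it tabulates all TEAEs and lacks only the interruption table. A reader might infer that the safety signal is lost; the laboratory part of it is kept.

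What does not stand is the suggestion that the other outputs make the gap harmless. They give a value and a tablet count, without causality, action or outcome. Leaving the matter to each site also means that the same course of events may be an AE at one site and not at another.

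Parts of the public protocol on safety management are blacked out or not included. The point rests on the readable text.

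**Conclusion.** The point holds in a limited form. A symptom-free, non-serious abnormal result that leads to temporary interruption and restart of study drug, with no change in concomitant therapy, is not required on the AE page. Protocol 3.4 and 3.6.2 are written as though it would be. For these subjects causality, action taken and outcome could be missing from the TEAE data.

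The frequency cannot be estimated from the documents. Any rate, for example 2–6% of an arm (0.02 × 50 = 1 to 0.06 × 50 = 3 subjects), would be an assumption without support there, and the point does not depend on it.

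A reader might go further and infer that the comparison between doses is biased or that a poorly tolerated dose would look clean. The documents do not show this. They contain no dose-selection rule based on AE tables, and the PCS and liver-test tables would still show the affected values. A reader might also infer that the absence of a CTCAE grade 3 recording trigger is itself an error. The gap comes from the missing word for interruption, and it closes without a grade trigger.

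The conclusion assumes that no blacked-out or separate instruction to sites already requires the record.

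**What to change.** 1. In Protocol 3.6.1, insert 'interruption or' before 'permanent' in the second condition, so that it covers both interruption and permanent discontinuation of study drug. Check the result against the general AE definition in 3.6.1, the restart text in 3.4 and the Drug Interrupted category in 3.6.2, so that all four say the same thing about recording.
2. In SAP 6.5.1, add a table or listing of TEAEs leading to interruption of study drug, by system organ class and preferred term.

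A recording trigger at CTCAE grade 3 and a field for CTCAE grade on the AE page are optional. They would help with the difference between the CTCAE grade and the functional severity scale, but they are not needed here.

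The cost is two inserted words, one SAP output and a few more laboratory AEs for sites to record. The change affects recording and reporting only and leaves every rule on dosing, interruption, restart and withdrawal as it is.

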3.6.2. Assessing Adverse Events

When completing appropriate forms for reporting the AE, the Investigator will be asked to assess the AE as follows:

Seriousness of Adverse Event:

- Serious: The AE meets a criterion of the SAE definition.
- Not Serious: The AE does not meet a criterion of the SAE definition.

Severity of Adverse Event:

- Mild: No interference with functioning.
- Moderate: No significant interference with functioning.
- Severe: Significant interference with functioning.

Relationship of Adverse Event (Causality):

The Investigator's causality assessment is the determination whether there is a reasonable possibility that the IMP caused or contributed to the adverse event. Generally, the facts (evidence) or arguments to suggest causal relationship should be documented. Factors to be taken into consideration when assessing causality include: subject's underlying and pre-existing conditions, prior/concomitant medications, timing of onset relative to study drug administration, the known PK characteristics of JTE-051, the currently-known safety profile of JTE-051, known class effects of similar MOA drugs, the de-challenge/re-challenge response (if available) and any other information that is considered relevant by the Investigator.

Akros Pharma Inc. evaluates the relationship of an AE to the study drug using the following three categories:

- Not Related
- Possibly Related
- Related

Action Taken with Regard to Study Drug:

Akros Pharma Inc. evaluates the action taken with the treatment product and/or interacting product using the following four definitions:

- Dose Not Changed: The subject was on treatment with the study drug when the AE occurred, and the study drug dosing was maintained at the same dose level
- Drug Interrupted: The subject was on treatment with the study drug when the AE occurred, and the study drug dosing was temporarily discontinued and then re-started
- Drug Withdrawn: The subject was on treatment with the study drug when the AE occurred, and the study drug dosing was permanently discontinued
- Not Applicable: The subject was not receiving treatment with the study drug when the AE occurred (i.e., AE occurred before the first study drug administration or after the last study drug administration)

Other Action Taken:

- None
- Additional Treatment Given for the AE
- Therapeutic/ Diagnostic Procedure
- Other (including discontinuation/reduction of a concomitant medication due to the AE)

Outcome to Date:

- Not Recovered/Not Resolved: The subject has not yet recovered from the AE; the event has not improved (follow-up of all serious AEs will be continued until the overall clinical outcome has been ascertained).
- Recovering/Resolving: The subject has not yet recovered from the AE, however, the event is improving (follow-up of all serious AEs will be continued until the overall clinical outcome has been ascertained).
- Recovered/Resolved: The subject recovered from the AE with no sequelae.
- Recovered/Resolved with Sequelae: The subject recovered from the AE with sequelae.
- Fatal: The subject's death was a result of the AE.

